5.4.1 Patients with Diabetes Mellitus

Patients with diagnosis of diabetes mellitus treated with insulin or oral hypoglycemic drugs needs to carefully monitor blood sugar level due to increased risk of hypoglycemia when treated with itraconazole and/or hydroxychloroquine. Patients with diabetes will be required to monitor and record the capillary blood sugar levels at least three times a day. Dose of insulin or oral hypoglycemic drugs will be adjusted accordingly.

5.5 **Duration of Therapy**

In the absence of treatment delays due to adverse event(s), treatment may continue as long as patient is benefitting or until one of the following criteria applies:

- Disease progression as defined by RECIST 1.1
- Clinical progression
- Women who become pregnant or are breast feeding
- Sexually active subjects who refuse to use medically accepted forms of contraception (e.g. male condom, female condom) during the study and for 30 days following

discontinuation of study treatment

- Intercurrent illness that prevents further administration of treatment
- Unacceptable adverse event(s)
- Significant non-compliance with the protocol schedule in the opinion of the investigator
- Patients requiring a delay in treatment beyond the allowed time frame
- Patients requiring more than 2 dose reductions of hydroxychloroquine or itraconazole
- Patient decides to withdraw from the study
- General or specific changes in the patient's condition render the patient unacceptable for further treatment in the judgment of the investigator
- Termination of the protocol by a regulatory agency or Sponsor-Investigator, or study medication can no longer be provided

5.6 **Duration of Follow Up**

Patients will be followed for 12 weeks after removal from study or until death, whichever occurs first. Patients removed from study for unacceptable adverse event(s) will be followed every 4 weeks by the clinic team until resolution or stabilization of the adverse event.

		Follow-Up Period			
		30-37 Days from the End of Study Drug Administration	Every 4 weeks (after the off study visit), up to 12 weeks	Until resolution or stabilization of treatment related adverse event(s)	RECIST 1.1 every 12 weeks from last scan until PD
from	Objective Disease Progression	X	X	X (FU every 4 weeks)	
Reason Patients Removed from study	Clinical Progression/ Symptomatic Deterioration	Х	Х	X (FU every 4 weeks)	

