son Patient str	Adverse Events or clinically significant lab value	Х	X	X (weekly FU for 4-weeks, then monthly)	X
Reas	All other patients	X	X	X (FU every 4 weeks)	X

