- c: Off-study evaluation and follow up as described in section 5.5
- d: Pre-treatment biopsy to be done up to 28 days prior to start of therapy. On-treatment biopsy to be done on day 8-14.
- e: Patients undergoing a biopsy or fluid collection for diagnostic or therapeutic reasons may have a sample of their tissue or fluid collected for the purposes of this study.
- f: Patients will be followed every 4 weeks from the End of Treatment visit for 12 weeks or until resolution of adverse events for patients who will come off study due to toxicity.
- g: Only patients who come off study treatment for reasons other than progressive disease (radiological or clinical) need to have scans and RECIST measurements performed. This will occur every 12 weeks from the previous scan until documented progression (radiological or clinical).
- h: Three 10 mL tubes of heparinized blood will be collected for PBMC and plasma isolation, and one 5 mL SST tube for sera.
- i: Samples must be drawn prior to MUGA.
- j. The following eye tests will be performed: Ocular Symptom Assessment, Visual Acuity, Slit Lamp Examination, Intraocular Pressure, Dilated Fundoscopic Examination, Schirmer test and any other diagnostic test.

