11. MEASUREMENT OF EFFECT

11.1 Antitumor Effect – Solid Tumors

Patients with measurable disease will be assessed by standard criteria. For the purposes of this study, patients should be re-evaluated for response every 8 weeks. In addition to a baseline scan, confirmatory scans should also be obtained at least 4 weeks following initial documentation of objective response.

In the expansion cohort, tumours will be re-evaluated every 8 weeks during treatment, and at least 4 weeks after the first observation of a complete or partial response. After discontinuation of protocol treatment, patients who have discontinued treatment for reasons other than disease progression will still be re-evaluated every 12 weeks.

Response and progression will be evaluated in this study using the new international criteria proposed by the revised Response Evaluation Criteria in Solid Tumors (RECIST) guideline (version 1.1) [Eur J Ca 45:228-247, 2009]. The published RECIST document is available at http://www.eortc.be/RECIST. Changes in the largest diameter (unidimensional measurement) of the tumor lesions and the shortest diameter in the case of malignant lymph nodes are used in the RECIST criteria.

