11.1.6 Progression-Free Survival

PFS is defined as the duration of time from start of treatment to time of progression or death, whichever occurs first.

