APPENDIX F DATA MANAGEMENT GUIDELINES

Data Management Guidelines

Case Report Form Submission Schedule

The Registration Checklist will be a paper CRF that will be provided by the Drug Development Central Office and all other data required for the study will be collected in eCRFs in Medidata. The form submission schedule is outlined below.

Case Report Form	Submission Schedule
Registration Checklist	At the time of registration
Baseline Form	Within 3 weeks of on study date
On Treatment Form	Within 3 weeks of the end of each cycle of
	treatment
Off Treatment Form	Within 3 weeks of the patient coming off-study
Short Follow-up Form	Within 3 weeks of the patient coming to clinic.
	Required every 4 weeks until 12 weeks post off-
	treatment visit.
Final Report Form	Within 3 weeks of the patient's completion on
	study

Case Report Form Completion

The paper Registration Checklist must be completed using black or blue ink. Any errors must be crossed out so that the original entry is still visible, the correction clearly indicated and then initialed and dated by the individual making the correction. eCRFs will be completed according to the schedule noted above.

All patient names or other identifying information will be removed prior to being sent to the Central Office and the documents labeled with patient initials, study number and the protocol number if applicable.

Monitoring

This is an investigator initiated study and study monitoring will be performed by the Drug Development Program Central Office or its designate.

Data in the Medidata Rave eCRFs will be monitored on a regular basis and quality assurance measures will be performed. Electronic data queries as well as paper query letters may be issued to the site.

Regulatory Requirements

• Please submit all required documents to the DDP Central Office.

- Canadian Principal Investigators must submit a completed Qualified Investigator Undertaking. The original signed copy is to be housed by the DDP Central Office.
- All investigators must have an up-to-date CV (signed within 2 years) on file with the DDP Central Office.
- Laboratory certification/accreditation and normal ranges are required
- Confirmation of all investigators having undergone training in the Protection of Human Research Subjects is required. It is preferred that other staff involved in the trial also undergoes such training.
- Investigators and site staff are required to complete Medidata eCRF training modules depending on delegated tasks

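### Section 5.6 ends follow-up at 12 weeks in its text but requires scans until progression in its table, so late PFS events can be lost in patients who stop without progression

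*Protocol*

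**What the plan says.** The passages that set a 12-week limit:

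- Protocol 5.6, text: "Patients will be followed for 12 weeks after removal from study or until death, whichever occurs first". The only extension given there is for unacceptable adverse events, until they resolve or stabilise.
- Section 10, footnote f: "Patients will be followed every 4 weeks from the End of Treatment visit for 12 weeks or until resolution of adverse events".
- Appendix F, Short Follow-up Form: "Required every 4 weeks until 12 weeks post off" (the off-treatment visit).

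The passages that continue tumour assessment:

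- Protocol 5.6, table column: "RECIST 1.1 every 12 weeks from last scan until PD". It is marked for patients removed for adverse events and for the row "All other patients". It is blank for the two progression rows.
- Section 10, footnote g: "This will occur every 12 weeks from the previous scan until documented progression (radiological or clinical").
- Section 11.1: "patients who have discontinued treatment for reasons other than disease progression will still be re-evaluated every 12 weeks", with no end date.

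Two further passages matter. Section 11.1.6 states: "PFS is defined as the duration of time from start of treatment to time of progression or death, whichever occurs first". Section 5.7 makes completed follow-up a reason for removal from study, whereas 5.6 starts the follow-up clock at removal.

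**The concern.** The patients concerned are those who stop treatment for toxicity or another reason without progression. For them the 5.6 sentence and the 5.6 table give different end points for observation. Read literally, the sentence ends observation at 12 weeks or death, whichever is earlier; the table ends it at progression.

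Median PFS is a secondary objective, runs to progression or death, and is estimated by Kaplan-Meier (13.4). A patient whose observation ends at 12 weeks is censored there, and a later progression or death is not counted. Duration of response (11.1.5) is exposed in the same way for a responder who stops for toxicity. Events that were never collected cannot be restored at analysis.

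The circular reference between 5.6 and 5.7 adds to the problem, because the date from which the 12 weeks run is not fixed. The 5.6 text counts from removal from study, and footnote f and Appendix F count from the visit after treatment ends.

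**Working it through.** The plan states no figure to reproduce, so the check is one of scan timing and of events lost.

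**1. Scans that fit within 12 weeks.** On-treatment scans are 8-weekly (11.1, 13.1.2). Let the last one be *s* weeks before stopping, with *s* from 0 to 8. Off-treatment scans are 12-weekly from the last scan, so scan *k* falls at 12*k* − *s* weeks after stopping.

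- First scan: 12 − 8 = 4 to 12 − 0 = 12 weeks.
- Second scan: 24 − 8 = 16 to 24 − 0 = 24 weeks.

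A limit of 12 weeks after stopping admits exactly one scan. If the 12 weeks run from the day 30–37 visit, the limit is 12 + 30/7 = 16.3 to 12 + 37/7 = 17.3 weeks after the last dose. A second scan then fits only if *s* is at least 24 − 16.3 = 7.7 or 24 − 17.3 = 6.7 weeks. If *s* is uniform over 0 to 8, that is 4% to 16% of cases.

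**2. Share still progression-free at that one scan.** Assume exponential PFS and use as residual medians the two figures in 2.2.1 from the retrospective platinum-resistant ovarian series (53 days for chemotherapy alone, 103 days with itraconazole). The scan is 84 days after the last one.

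- 2^(−84/53) = 0.33
- 2^(−84/103) = 0.57

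**3. Events lost.** The phase II maximum is 34 patients (13.2). The stopping rate is an assumption. The lower value, 14%, is the share that left the 600 mg/day itraconazole arm cited in 2.2.1 because of toxicity (4 patients, one of them not drug related). The upper value, 30%, allows for other reasons.

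- Stoppers: 0.14 × 34 = 4.8; 0.30 × 34 = 10.2.
- At 14%: 4.8 × 0.33 = 1.6 to 4.8 × 0.57 = 2.7 events.
- At 30%: 10.2 × 0.33 = 3.4 to 10.2 × 0.57 = 5.8 events.

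These products are on the high side, because they assume that every intended stopper is still progression-free when stopping. A simulation relaxes this: 34 patients, stopping time uniform over 0 to 16 weeks, stopping counted only if it precedes progression, and observation cut 12 weeks after stopping. The average loss was:

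| Median PFS | 14% stop | 30% stop |
|---|---|---|
| 53 days | 0.8 | 1.8 |
| 103 days | 1.9 | 4.0 |

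About 1 to 5 of 34 is a fair summary.

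**4. Effect on the median.** In the same simulation the Kaplan-Meier median did not change at 53 days and changed by at most about 0.2 weeks on average at 103 days. Doubling the hazard after stopping, so that stopping is prognostic, still moved it by no more than about 0.1 weeks. With a longer assumed median of 6 months and 10% to 30% stopping, it was 5.7–5.8 months with follow-up to progression and 5.9–6.0 months with the 12-week limit.

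**The case against.** The strongest reply is that the two duties are already separate. The 5.6 table has one column for 4-weekly visits up to 12 weeks and another for scans until progression; footnotes f and g make the same split, and 11.1 sets no 12-week limit on re-evaluation. Visits can end while scans continue, and no passage says that scans stop at 12 weeks. This stands as the likely intent, and the two rules are not impossible to carry out together. It does not remove the problem: the 5.6 sentence covers follow-up without qualification, and the only recurring follow-up form stops with it.

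A reader might also infer four stronger points, which the documents do not support.

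- *Later events have nowhere to be recorded.* Appendix F also has a Final Report Form at completion on study, and 5.7 lists death as a removal reason to be documented with its date. What is missing is a scheduled form for scans and progression after week 12.
- *PFS will differ between sites.* Section 13.1.2 calls the phase II cohort single-centre. Inconsistent handling between patients is as far as the text goes.
- *PFS will be overstated.* At the protocol's own cited medians the Kaplan-Meier median hardly moves. Bias needs stopping to be prognostic, which is possible but not shown.
- *The change from 8-weekly to 12-weekly scans is an error.* The 5.6 table, footnote g and 11.1 state the off-treatment interval consistently, so it is a choice.

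Patients who withdraw from the study itself may be out of reach under any wording. Detailed censoring rules may properly sit in an SAP that is not at hand.

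**Conclusion.** The point holds as a minor inconsistency in current text. The 5.6 sentence and the Appendix F form schedule end follow-up at 12 weeks; the 5.6 table and footnote g require scans until progression, and 11.1 sets no end. Sections 5.6 and 5.7 also define removal and follow-up in terms of each other.

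If the sentence is followed, a patient who stops without progression has one off-treatment scan, and about 1 to 5 of 34 PFS events are lost. That range rests on assumed stopping rates of 14% to 30%, exponential PFS, and medians borrowed from another treatment setting. The median itself would shift by less than 0.4 weeks at those medians, so the cost is in events and precision. The MTD and the two-stage response design are largely untouched.

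**What to change.** Reconcile the passages in one amendment:

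- In the 5.6 text, limit the 12-week period to the 4-weekly visits and name the date from which it runs.
- State there that patients who stop without progression continue tumour assessment and have death status recorded until progression or death. The scans are already required by the table and footnote g; death status follows from the PFS definition in 11.1.6.
- Align footnote f and 5.7 with this, so that follow-up is not complete while scans are still due and removal from study no longer both starts and ends follow-up.
- Add to the Appendix F schedule a form for scans, progression and death after week 12.

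The cost is amendment wording and one eCRF page. No scans are added beyond those that the table and footnote g already require.

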5.7 Criteria for Removal from Study

Patients will be removed from study when any of the criteria listed below applies:

- Patient death
- Follow up complete
- Termination of the study by regulatory authorities
- Termination of the study by the Sponsor-Investigator

The reason for study removal and the date the patient was removed must be documented in the Case Report Form.

6. DOSING DELAYS/DOSE MODIFICATIONS

Doses will be reduced for haematological and other adverse events. Dose adjustments are to be made according to the greatest degree of toxicity. Adverse events will be graded using the NCI Common Terminology Criteria for Adverse Events Version 4.0 (CTCAE).

When a dose is held due to adverse events, the cycle shall continue even if no study medication is received.

The guidelines which follow outline dose adjustments for several of these toxic effects. If a patient experiences several adverse events and there are conflicting recommendations, please use the recommended dose adjustment that reduces the dose to the lowest level.

The major adverse effects of itraconazole and hydroxychloroquine are listed in section 7.

Dose reduction for itrozanole as specified in Table below:

Dose Level	itraconazole
1	300 mg PO BID
-1	200 mg PO BID
-2	100mg PO BID

For dose adjustment of hydroxychloroquine, please refer to dosing guidelines from the phase I component of trial in section 5.2.

Note that patients cannot dose reduce below 200mg OD for hydroxychloroquine and 100 mg BID for itraconazole. Any patients who experience adverse events requiring hydroxychloroquine dose reduction below 200 OD mg or itraconazole below 100 mg BID will stop study related therapy.

Nausea	Management/Next Dose for itraconazole	Management/Next Dose for hydroxychloroquine	
≤ Grade 1	No change in dose	No change in dose	
Grade 2	Hold* until \leq Grade 1. Resume at	Hold* until \leq Grade 1. Resume at	
Grade 2	same dose level.	same dose level.	
Grade 3	Hold* until < Grade 2. Resume at	Hold* until < Grade 2. Resume at	
Grade 3	one dose level lower, if indicated.**	one dose level lower, if indicated.**	
		Off protocol therapy	
*Patients requiring a delay of >2 weeks should go off protocol therapy.			

^{**}Patients requiring > two dose reductions should go off protocol therapy.

Recommended management: Antiemetics and intravenous hydration if required.

Vomiting	Management/Next Dose for	Management/Next Dose for	
vointing	itraconazole	hydroxychloroquine	
≤ Grade 1	No change in dose	No change in dose	
Grade 2	Hold* until \leq Grade 1. Resume at	Hold* until \leq Grade 1. Resume at	
Grade 2	same dose level.	same dose level.	
Grade 3	Hold* until < Grade 2. Resume at	Hold* until < Grade 2. Resume at	
Grade 3	one dose level lower, if indicated.**	one dose level lower, if indicated.**	
Grade 4	Off protocol therapy	Off protocol therapy	
*D.:			

^{*}Patients requiring a delay of >2 weeks should go off protocol therapy.

Recommended management: Antiemetics and intravenous hydration if required.

Diarrhea Management/Next Dose for itraconazole		Management/Next Dose for hydroxychloroquine
≤ Grade 1	No change in dose	No change in dose
Grade 2	Hold* until ≤ Grade 1. Resume at same dose level.	Hold* until \leq Grade 1. Resume at same dose level.
Grade 3	Hold* until < Grade 2. Resume at one dose level lower, if indicated.**	Hold* until < Grade 2. Resume at one dose level lower, if indicated.**
Grade 4	Off protocol therapy	Off protocol therapy

^{*}Patients requiring a delay of >2 weeks should go off protocol therapy.

Recommended management: Loperamide antidiarrheal therapy

Dosage schedule: 4 mg at first onset, followed by 2 mg with each loose motion until diarrhea-

free for 12 hours (maximum dosage: 16 mg/24 hours)

Adjunct anti-diarrheal therapy is permitted and should be recorded when used.

Neutropenia	Management/Next Dose for itraconazole	Management/Next Dose for hydroxychloroquine
≤ Grade 1	No change in dose	No change in dose
Grade 2	Hold* until ≤ Grade 1. Resume at same dose level.	Hold* until \leq Grade 1. Resume at same dose level.
Grade 3	Hold* until < Grade 2. Resume at one dose level lower, if indicated.**	Hold* until < Grade 2. Resume at one dose level lower, if indicated.**
Grade 4	Off protocol therapy	Off protocol therapy

^{*}Patients requiring a delay of >2 weeks should go off protocol therapy.

^{**}Patients requiring > two dose reductions should go off protocol therapy.

Anemia	Management/Next Dose for itraconazole	Management/Next Dose for hydroxychloroquine
≤ Grade 1	No change in dose	No change in dose
Grade 2	No dose reduction or delay for anemia is required. The investigator can	

^{**}Patients requiring > two dose reductions should go off protocol therapy.

^{**}Patients requiring > two dose reductions should go off protocol therapy.

Anemia	Management/Next Dose for itraconazole	Management/Next Dose for hydroxychloroquine
Grade 3	elect to dose reduce or hold the treatment, if considered clinically	
Grade 4	indicated. Blood transfusion is allowed at each time during the study (screening, treatment and follow-up).	

Thrombocytopenia	Management/Next Dose for itraconazole	Management/Next Dose for hydroxychloroquine
≤ Grade 1	No change in dose	No change in dose
Grade 2	Hold* until \leq Grade 1. Resume at	Hold* until \leq Grade 1. Resume at

7. ADVERSE EVENTS

The adverse drug reactions are ranked by frequency, using the following convention:

- Common ($\ge 1/100$ to < 1/10)
- Uncommon ($\ge 1/1,000$ to < 1/100)
- Rare ($\geq 1/10,000 \text{ to} < 1/1,000$)
- Very rare (< 1/10,000)
- Not known (cannot be estimated from the available data)

7.1 List of Adverse Events and Reporting Requirements

This study will utilize the CTCAE version 4.0 for toxicity and Adverse Event reporting. A copy of the CTCAE version 4.0 can be downloaded from the CTEP home page (http://ctep.cancer.gov). All appropriate treatment areas should have access to a copy of the CTCAE version 4.0.

7.1.1 Expected Adverse Events and Protocol-Specific Expedited Adverse Event Reporting for Investigational Agent(s)

Adverse event (AE) monitoring and reporting is a routine part of every clinical trial. The following list of AEs (Sections 7.1.1.1 and 7.1.1.2) and the characteristics of an observed AE (Section 7.2) will determine whether the event requires expedited reporting as an SAE in addition to routine reporting.

In addition, hospitalizations for routine procedures, protocol treatment, blood sampling, investigations and tissue biopsies are NOT considered SAE in this protocol.

7.1.1.1 Expected Adverse Events using Itraconazole

Blood and Lymphatic System	Very rare: Leucopenia and neutropenia,
Disorders	thrombocytopenia
Immune System Disorders	Very rare: Serum sickness, angioneurotic
	oedema, anaphylactic, anaphylactoid and
	allergic reactions
Metabolism and Nutrition Disorders	Rare: Hypertriglyceridemia,
	hypokalaemia
Nervous System Disorders	Very rare: Peripheral neuropathy,
	paraesthesia, hypoaesthesia, headache,
	dizziness
Eye Disorders	Very rare: Visual disturbances, including
	vision blurred and diplopia
Ear and Labyrinth Disorder	Very rare: Tinnitus, transient or
	permanent hearing loss

Cardiac Disorders	Rare: Chest pain
	Very rare: Congestive heart failure
Respiratory, Thoracic and Mediastinal	Very rare: Pulmonary oedema, dyspnoea
Disorders	
Gastrointestinal Disorders	Very rare: Pancreatitis, abdominal pain,
	vomiting, dyspepsia, nausea, diarrhoea,
	constipation, dysgeusia
Hepatobiliary Disorders	Very rare: Serious hepatotoxicity
	(including some cases of fatal acute liver
	failure), hepatitis, reversible increases in
	hepatic enzymes
Skin and subcutaneous tissue disorders	Very rare: Toxic epidermal necrolysis,
	Stevens-Johnson syndrome, actue
	generalised exanthematous pustulosis,
	erythema multiforme, exfoliative
	dermatitis, leukocytoclastic vasculitis,
	urticaria, alopecia, photosensitivity, rash,
	pruritus
Musculoskeletal and Connective Tissue	Very rare: Myalgia, arthralgia
Disorders	
Renal and Urinary Disorders	Very rare: Pollakiuria, urinary
	incontinence
Reproductive System and Breast	Very rare: Menstrual disorders, erectile
Disorders	dysfunction
General Disorders	Very rare: Oedema, pyrexia

